**Fish Oil-derived N-3 Polyunsaturated Fatty Acids
and Extracellular Vesicles
(NCT03203512)**

Study Protocol

Feb 2017

Study objectives

The main objectives of the study were divided into two strands (**Figure 1**).

[figure not shown]

Figure 1. Overview of the experimental work. Strand 1 focused on the numeration and functional analysis of circulating EVs; strand 2 focused on the numeration and functional analysis of platelet-derived EVs. EVs, extracellular vesicles; PDEVs, platelet-derived EVs.

Strand 1: the influence of n-3 PUFA supplementation on the number and phenotype of total circulating EVs, and their fatty acid composition and coagulatory activities.

Strand 2: the influence of n-3 PUFA on the production of EVs by platelets taken from subjects and generated *in vitro* as well as their fatty acid composition and coagulatory activities.

Study design

The study was a randomised, double-blind, controlled crossover intervention. A total of 40 subjects aged between 40 and 70 years with moderate CVD risk (see criteria below) were recruited and randomly allocated to consume either fish oil or control (high-oleic safflower oil) in the first 12-week intervention period. After a 12-week washout, they then crossed over to the other intervention for a further 12 weeks. Random assignment of subjects for intervention order ("1" and "2") was performed using online software (<https://www.randomizer.org/>). Fish oil and control capsules were of identical appearance and blinded by an individual not involved in the study. All investigators involved in the study remained blind until all sample and statistical analysis had been completed.

The length of the intervention and washout periods was based on evidence that incorporation of n-3 PUFA in all cell types reaches a plateau after 12 weeks' intervention and that a 12- week washout period is sufficient to avoid carryover effects (Walker et al., 2015).

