During the study, there were four intervention visits, which took place at the beginning and end of each 12-week intervention period (weeks 0, 12, 24 and 36). Before each study visit, subjects were asked to abstain from alcohol and strenuous exercise during the 24 hours prior to the study day. On each visit day, subjects were asked to come to the nutrition unit in an unfed state (fasted, not eating or drinking anything but water from 8 pm the night before). After taking height, weight and blood pressure measurements, a blood sample of approximately 100 ml was collected into vacutainer tubes containing 3.2% sodium citrate (Greiner Bio-One, Gloucestershire, UK) for EV-related analysis (details see below). After the first visit, subjects were asked to start to consume 6 capsules per day of either fish oil (Wiley's Finest Easy Swallow Minis, Canada), providing a total daily intake of 1.8 g n-3 PUFA, or high-oleic safflower oil (Wiley's Finest, Canada), providing 740mg oleic acid + 120mg linoleic acid per day. Subjects were advised to take capsules with breakfast, lunch and dinner (2 at each meal). Weeks 12-24 represented a washout period and then subjects crossed over to the other intervention product until week 36 (**Figure 2**).

Subjects were asked to complete food frequency questionnaires at home before their first visit and again during each arm of the intervention study (weeks 0, 12, 24 and 36). These were used to assess their habitual diet and to confirm that they had low consumption of oily fish (less than one portion per month).

[figure not shown]

Figure 2. Study timeline

Study methods

Blood collection and processing

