The impact of PDEVs (before and after intervention) on fibrin clot formation in VFP was assessed in 96-well flat-bottom microplates (Greiner Bio-One, Stonehouse, Gloucestershire, UK) by a change in turbidity of the VFP at 405 nm (A405) every 30 seconds, for 1 hour at 37°C using a Flex Station 3 plate reader (Molecular Devices, United State). Therefore, pooled PFP (positive control) and VFP (negative control), served as benchmarking in this assay. The assay was then set up by diluting 30% of VFP in clot buffer (10 mM Tris [pH 7.4] and 0.01% Tween 20) and 5 µg/ml protein concentration of PDEVs (final concentration) was then added. Fibrin clot formation was initiated by addition of 5 mM CaCl2 in a final volume of 100 µl of clotting mixture. Plates were read at 37 °C for 1 hour at 30 second intervals using a fluorescence plate reader (FlexStation 3, United State) at wavelength of 405 nm. Data were then analysed by an online application (https://drclongstaff.shinyapps.io/Clot_or_HaloCL/) to obtain relative parameters: time to 50% change, absorbance at 50% change, absorbance at peak, area under curve.

Measurement of thrombin generation

Thrombin formation was assessed using a commercially available, plate-based thrombin generation assay (Technothrombin TGA kit, Austria), which assesses a change in fluorescence as a result of cleavage of a fluorogenic substrate by thrombin over time upon activation of the clotting cascade by tissue factor. Two separate analyses were conducted: (i) determination of the effect of n-3 PUFA supplementation on thrombin generation in PFP from study samples relative to VFP and (ii) determination of the effects of *in vitro*-generated PDEVs or circulating EVs derived from study samples on thrombin generation in VFP. Prior to analysis, a thrombin calibration curve was constructed from dilutions of lyophilised Hepes-NaCl-buffer containing 0.5 % bovine serum albumin and ~ 1000 nM thrombin in buffer with BSA. A kinetic reading of a plate was initiated by additional of 50 µl of fluorogenic substrate solution containing fluorogenic substrate 1 mM Z-G-G-R-AMC and 15 mM CaCl2.

Calibration curves were recorded at 37 °C for 10 minutes with 30 seconds intervals using the plate reader (FlexStation 3, United State) at 360 nm for excitation and at 460 nm for emission.

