Feb 2017

Statistical analysis

Data are expressed as mean \pm SEM if normally distributed and as median with interquartile range when not. The Kolmogorov-Smirnov test was applied to assess the normal distribution of continuous variables and all variables with non-normal distribution were log-transformed to achieve normal distribution before analysis. A general linear model with fixed factors of treatment and period was conducted to determine the differences in the effect of two treatments and two periods on biological characteristics and EVs parameters. A paired t-test comparing the baseline data (before fish oil and before control oil) was performed to check potential carry-over effects. All statistical analyses were performed with SPSS Statistics version 25 and a *p*-value < 0.05 was considered statistically significant.

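### Period baselines are collected at weeks 0 and 24, but the treatment model lists no baseline covariate and does not define its response, so available precision may be lost

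*Combined protocol and SAP*

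**What the plan says.** The protocol (Study design) describes a two-period crossover: "The study was a randomised, double-blind, controlled crossover intervention". It has 40 subjects. On timing it says that "there were four intervention visits, which took place at the beginning and end of each 12-week intervention period (weeks 0, 12, 24 and 36"). At each visit, "After taking height, weight and blood pressure measurements, a blood sample of approximately 100 ml was collected" for the vesicle assays. Weeks 0 and 24 are thus period-specific baselines for the week 12 and week 36 values. One assay is explicitly described as before-and-after: "The impact of PDEVs (before and after intervention) on fibrin clot formation in VFP" (Measurement of clot formation induced by PDEVs).

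The SAP (Statistical analysis) gives one treatment model: "A general linear model with fixed factors of treatment and period was conducted to determine the differences in the effect of two treatments and two" [...]. No covariate, subject term or sequence term is listed, and the response variable is not defined. Baselines are mentioned once: "A paired t-test comparing the baseline data (before fish oil and before control oil) was performed to check potential carry-over effects". Neither document gives a power calculation, an effect size, an SD or a within-subject correlation.

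**The concern.** A period baseline can sharpen a crossover comparison in a way that a subject term cannot. The subject term removes a person's constant level. The period baseline can also remove drift within a person between the two end-of-period visits, which are 24 weeks apart, for example from season, diet or body weight. If the week 0 and week 24 values are left out of the model, that information goes unused although the visits and samples are already in the design. With 40 subjects, a real fish-oil effect is then more likely to be missed.

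The undefined response adds to this. End value, change from baseline and baseline-adjusted end value are all compatible with the SAP's sentence. They differ in efficiency, and the choice is left to the analyst.

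**Working it through.** **Inputs.** From the documents: 40 subjects, two periods, visits at weeks 0, 12, 24 and 36, and a 0.05 significance level. Assumed: 20 subjects per sequence, two-sided testing, equal SD at all visits, and every correlation. The plan has no power figure to reproduce.

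**Notation.** r12, r24 and r36 are the correlations between measurements 12, 24 and 36 weeks apart. D is the difference between a subject's two end-of-period values. B is the difference between the same subject's two period baselines.

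**Formulas (within-subject analysis, variance per subject in SD² units).**
- End values only: 2(1 − r24).
- Correlation of D with B: c = (r12 − r36) / [2(1 − r24)].
- Baseline-adjusted: 2(1 − r24)(1 − c²).
- Change scores: 4(1 − r24) − 2(r12 − r36).

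Under equal correlation r12 = r36, so c = 0 and adjustment gains nothing. Under autoregressive correlation a per 12 weeks, c = (a − a³) / [2(1 − a²)] = a/2.

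**Example, a = 0.7.** End values: 2(1 − 0.49) = 1.02. c = 0.35, so the adjusted variance is 1.02 × (1 − 0.1225) = 0.895, a 12% reduction. Change scores: 4 × 0.51 − 2(0.7 − 0.343) = 1.326, which is 1.3 times the end-value variance.

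**Power with subject fitted.** The starting point is 80% for unadjusted end values (38 df). The noncentrality is rescaled by 1/√(1 − c²), with 37 df after adjustment. Change scores use the variance ratio and 38 df.

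| Assumed correlation | c | Variance reduction | Power, adjusted | Change-score variance ÷ end-value variance | Power, change score |
|---|---|---|---|---|---|
| Equal | 0 | 0% | 79.9% | 2.0 | 51% |
| Autoregressive 0.5 | 0.25 | 6% | 82.4% | 1.5 | 63% |
| Autoregressive 0.7 | 0.35 | 12% | 84.8% | 1.3 | 69% |
| Autoregressive 0.9 | 0.45 | 20% | 88.0% | 1.1 | 76% |

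**Simulated power** (40 subjects, true effect 0.5 SD, end-of-period response, 3,000 runs per row):

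| Assumed correlation | As written | + baseline | + subject | Both |
|---|---|---|---|---|
| Equal 0.5 | 64% | 74% | 87% | 86% |
| Autoregressive 0.5 | 61% | 72% | 70% | 73% |
| Autoregressive 0.7 | 63% | 86% | 86% | 89% |

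The as-written column is low because that model treats each subject's two values as independent. When they are positively correlated its test is conservative: at equal correlation 0.5 with no true effect, it rejects less than 1% of the time.

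**The case against.** The strongest reply is that the large gains belong mainly to the missing subject term. This stands. Adding subject alone recovers more than the baseline under equal correlation (87% against 74%), about the same under autoregressive 0.7, and slightly less under autoregressive 0.5. An end-value analysis within subject, without baselines, is valid and unbiased in a randomised crossover. The baseline is then a refinement that pays only if measurements within a period correlate more strongly than measurements in different periods. Across 24 weeks such decay is plausible, but the documents do not establish it.

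A reader might also infer more than the text supports:
- **That the baselines serve the carry-over test and nothing else.** This is not established. With the response undefined, the model may have been run on change from baseline. That would use the baselines, though less efficiently than end values in every case computed.
- **That precision is certainly discarded.** Under equal correlation with subject fitted, none is.
- **That every outcome has a baseline in each period.** The protocol schedules vesicle blood, weight and blood pressure at all four visits. It gives no assay-by-visit schedule for lipids, glucose, aggregation or thrombodynamics.

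**Conclusion.** The point holds in conditional form, for outcomes measured at all four visits. The treatment model as written has no baseline covariate and an undefined response, so precision obtainable from planned measurements may be lost. Against the model as written, adding the baseline is worth roughly 10 to 23 power points in the three scenarios simulated, but most of that is also obtained by fitting subject. Beyond a subject term, the baseline is worth nothing under equal correlation (a loss of about 1 point or less) and 2 to 8 points from 80% under autoregressive correlation of 0.5 to 0.9 per 12 weeks. These sizes rest wholly on assumed correlations and, in the simulation, on an assumed effect of 0.5 SD. The omission itself is plain from the text. It concerns efficiency and pre-specification, not bias.

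**What to change.** In the SAP's Statistical analysis section:
- Define the response as the end-of-period value (weeks 12 and 36).
- Replace the two-factor model with one containing subject, treatment, period and the same variable's period baseline (weeks 0 and 24), on the same scale as the response, so log-transformed if the response is.
- If subject is random, also enter the subject's mean baseline, so that the within-subject and between-subject slopes are not forced to be equal.
- State that raw change from baseline will not be used as the response in place of the covariate.
- Name the outcomes measured at all four visits, to which this applies.

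The change needs a few sentences and a revised model specification in SPSS, with no new visit, sample or subject. Relative to a model with subject already fitted, it uses one degree of freedom, or two with the mean-baseline term. That costs about 1 power point or less if the baselines prove uninformative.

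### The paired-baseline carry-over check ignores any shift between week 0 and week 24, so it can miss carry-over and, with clearly unequal sequences, imitate it

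*Combined protocol and SAP*

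**What the plan says.** Under Study design, the protocol describes a two-period crossover with 12-week interventions and a 12-week washout; visits fall at weeks 0, 12, 24 and 36. The two baselines are therefore week 0 and week 24. The protocol cites a published source for the view that a 12-week "washout period is sufficient to avoid carryover effects".

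On allocation, it says "Random assignment of subjects for intervention order" was done with online software. It gives no ratio, blocking or number per sequence. The total is 40 subjects.

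The SAP (Statistical analysis) gives one check on carry-over: "A paired t-test comparing the baseline data (before fish oil and before control oil) was performed to check potential carry-over effects". For the treatment comparison it says "A general linear model with fixed factors of treatment and period was conducted". Period is thus allowed for in the main model, but nothing applies that model to the baselines.

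**The concern.** For a subject who took fish oil first, the baseline before fish oil is week 0 and the baseline before control is week 24. For a subject who took control first, it is the other way round. The paired test pools both groups without a period or sequence term. Anything that moves everyone between week 0 and week 24, such as season, assay drift, or changed habits after enrolment, is mixed into the comparison with opposite signs in the two sequences.

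This matters because the trial has no other check, in its own data, that the washout was long enough. If a shift exists, a non-significant result reflects the shift and the split as well as carry-over, and may be read as more reassuring than it is.

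**Working it through.** **Inputs.** From the documents: 40 subjects, baselines at weeks 0 and 24, significance at 0.05. Assumed, because the documents do not give them: a two-sided test; a baseline SD of 1; a correlation rho between the two baselines of 0.7 or 0.5; carry-over from fish oil at week 24 of L = 0.5 SD relative to control; a common week 0 to week 24 shift pi between -1 and +1 SD; a share p of subjects taking fish oil first. There is no figure in the plan to reproduce.

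**Algebra.** Let D be the baseline before control minus the baseline before fish oil.

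- Fish oil first: D is week 24 minus week 0, with mean pi + L.
- Control first: D is week 0 minus week 24, with mean -pi.
- Pooled mean: p(pi + L) - (1 - p)pi = pL + (2p - 1)pi.
- Pooled variance: s² + p(1 - p)(2pi + L)², where s² = 2(1 - rho). At p = 0.5 the added term is (pi + L/2)².

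The comparison that removes pi is the difference between sequences in the week 24 minus week 0 change. Its mean is (pi + L) - pi = L.

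**Equal sequences, rho = 0.7, no shift.** Here s² = 0.6.

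- Paired test: mean 0.25, standard error sqrt((0.6 + 0.0625)/40) = 0.129, ratio 1.94.
- Between sequences: mean 0.5, standard error sqrt(0.6 × (1/20 + 1/20)) = 0.245, ratio 2.04.

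Halving the mean costs almost nothing, because the standard error roughly halves too.

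**Equal sequences, shift of +0.5 SD.** The added variance is (0.5 + 0.25)² = 0.5625. The paired standard error becomes sqrt(1.1625/40) = 0.170 and the ratio falls to 0.25/0.170 = 1.47. The between-sequence ratio stays at 2.04.

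**Power by simulation, 20:20, L = 0.5 SD:**

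| Shift (SD) | -1 | -0.5 | -0.25 | 0 | +0.25 | +0.5 | +1 |
|---|---|---|---|---|---|---|---|
| Paired, rho 0.7 | 23% | 47% | 51% | 47% | 36% | 23% | 4% |
| Between sequences, rho 0.7 | 51% | 51% | 51% | 51% | 51% | 51% | 51% |
| Paired, rho 0.5 | 18% | 32% | 34% | 32% | 26% | 18% | 5% |
| Between sequences, rho 0.5 | 34% | 34% | 34% | 34% | 34% | 34% | 34% |

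Shifts between -0.5 and 0 cost little. Shifts in the direction of the carry-over, or large ones in either direction, cost much more.

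**Unequal sequences, rho = 0.7, L = 0.5 SD (fish oil first : control first):**

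| Split | Shift (SD) | Mean of D = pL + (2p - 1)pi | Paired | Between sequences |
|---|---|---|---|---|
| 24:16 | 0 | 0.30 | 63% | 50% |
| 24:16 | +0.5 | 0.30 + 0.10 = 0.40 | 68% | 50% |
| 18:22 | +0.5 | 0.225 - 0.05 = 0.175 | 9% | 51% |
| 16:24 | 0 | 0.20 | 32% | 50% |
| 16:24 | +0.5 | 0.20 - 0.10 = 0.10 | 3% | 50% |

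**False alarms with no carry-over (L = 0), rho = 0.7.** At 20:20 a shift makes the paired test conservative (0.15% rejections at a 1 SD shift). At 23:17 it rejects no more than 5%. At 24:16 with a 0.5 SD shift it rejects 6.5%. For shifts of 0.5 to 1 SD it rejects 9 to 12% at 25:15 and 13 to 23% at 26:14.

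**How likely is imbalance?** If assignment was simple randomisation (an assumption), the sequence sizes differ by 4 or more with probability 64%, by 8 or more with 27%, and by 12 or more with 8%.

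**What undetected carry-over does to the treatment estimate.** With carry-over a at week 24 and b at week 36, end-of-period values are biased by -b/2 and change scores by (a - b)/2. For a = 0.5 SD, change scores are biased by 0.25 SD if it has gone by week 36 (b = 0). End values are biased by 0.25 SD in size if it is fully present (b = 0.5), and not at all if it has gone.

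**The case against.** The strongest reply is that the harm depends on quantities nobody has shown to exist. With no shift and equal sequences, the planned test has 47% power against 51%, and shifts from -0.5 to 0 SD cost almost nothing. With more subjects taking fish oil first, the planned test can reject more often than the alternative. False alarms matter only at splits of about 25:15 or worse, which simple randomisation would give about 15% of the time. All of this stands, and it limits the point to a conditional one. The higher power at 24:16 is no merit, though: it comes from the split and the shift, and at 16:24 the same mechanism works the other way.

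It is also true that the bias in the treatment estimate comes from carry-over, not from the test, and that the SAP ties no decision to the check. A better check would leave the treatment estimate, its standard error and its p-value as they are. What it changes is what can be said about carry-over.

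The alternative is itself only modestly powered. Its 95% confidence interval has a half-width of about 0.50 SD at rho 0.7 (2.024 × 0.245) and 0.64 SD at rho 0.5, so neither test can show that carry-over is absent. That is a reason to report the interval rather than a reason to keep the paired test.

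Finally, the protocol handles carry-over mainly by design, through the washout and its cited source. That makes carry-over less likely, but it does not repair the test meant to check it.

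**Conclusion.** The concern holds. The check leaves out the period term that the main model includes, and nothing else in the documents makes up for it. That much follows from the text and the algebra alone.

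How much it matters depends on the shift, the split, the correlation and the carry-over, none of which the documents give. Under the assumptions above, the main risk is missed carry-over: at 20:20 a shift of +0.5 SD cuts power from 47% to 23%, and at 16:24 it leaves 3%. Imitating carry-over is a lesser risk, confined to marked imbalance. If there is no shift and the sequences are equal, little is lost. The change should be made because it is a better method at almost no cost, not because the planned test is known to have failed.

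**What to change.** Replace the carry-over sentence in the SAP with: 'Differential carry-over will be estimated as the difference between sequences in the week 24 minus week 0 change (two-sample comparison), on the scale used in the main model, and reported with its 95% confidence interval. A non-significant result will not be taken as evidence that carry-over is absent.'

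Report the number of subjects in each sequence. Separately, state whether the response in the general linear model is the end-of-period value or the change from baseline, since this decides how any carry-over would reach the treatment estimate.

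The cost is SAP wording and one re-run comparison. The week 0 and week 24 measurements are already part of the study, so no new visits or assays are needed.
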